Efficacy of Two Novel Behavioral Post-cessation Weight Gain Interventions

NCT03156660

Document Uploaded 21APR2022

Document Created JAN2019

Statistical Analysis

All of the analyses will be performed with SAS/STATv14.1. Data will be examined for distributional normality and outliers prior to any analyses. Descriptive statistics will be generated for all variables of interest included in the analysis, overall and by treatment arm. Univariate comparisons will consist of χ^2 tests and ANOVA. We will use similar analytical methods to compare baseline characteristics between study completers and non-completers at 12 months. Based on these findings appropriate adjustments will be implemented in the regression models.

Consistent with previous studies, outcomes will be analyzed on an intention-to-treat basis, including available data from all randomized cases, regardless of treatment adherence and smoking status. Missing outcome data will be imputed using Markov Chain Monte Carlo model based approach by treatment arm. Monotone missing data pattern will be created by using all available measured outcome data points. This approach is most suitable for an arbitrary missing data mechanism.

Our hypotheses include that randomization to the SMALL and LOSS conditions will produce smaller post-cessation weight gain compared to participants in the BIBLIO condition. The main independent variable of interest will be treatment assignment and the outcome will be weight change from baseline to 12-month follow-up. Measures of weight will be obtained at multiple time points to provide feedback, but we will model only the final measure to capture full post-cessation weight gain. Two separate general linear and mixed ANCOVA-like regression models for continuous measures will be utilized, with treatment effect estimated as the distance between the fitted group-specific means at the 12-month data collection visit (SMALL compared to BIBLIO and LOSS compared to BIBLIO), while adjusting for the fitted distance between them at baseline. In addition, we will adjust within the model for demographic factors, baseline weight, and other covariates if needed; however, due to randomization, we do not anticipate significant differences in baseline distributions. We will also test the interactions between treatment assignment and demographic covariates to examine the homogeneity of treatment effects. We will include smoking status within our modeling strategy either as moderator or a confounder. We hypothesize no significant difference in post-cessation weight gain between the SMALL and LOSS conditions. We will compare the two conditions within the scope of the regression models described previously. The main treatment comparison results will be considered significant at $\alpha = .017$ due to three pre-planned contrasts, with all other associations at $\alpha = .05$.

We hypothesize that participants randomized to the SMALL, LOSS, and BIBLIO conditions will have similar rates of smoking cessation at 12-month assessment. Given that the outcome is binary (i.e., prolonged abstinence; yes or no) and the treatment conditions are nominal, we will use categorical analytical methods. To test the differences in prolonged abstinence between the intervention arms, we will apply χ^2 test and then a multivariate logistic regression model, with BIBLIO selected as the referent group compared to the other conditions. We will estimate the relative odds of a treatment effect on prolonged abstinence while adjusting for baseline demographics, smoking history (e.g., onset of regular smoking, quit attempts, use of tobacco products), process measures and other potential confounders. As such, we can test the associations and estimate effects of additional variables, besides treatment effect.

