testing both of these interventions against a comparison group receiving the smoking cessation intervention with bibliotherapy support, we will move the field forward in identifying the most promising approaches to reducing postcessation weight gain.

Another novel feature of the proposed study is our target population. While previous studies have largely focused on women (16), we will have targeted recruitment of men, so that we recruit both men and women to this study, to facilitate the generalizability of our findings. In addition, men were found in previous research (32) to be more likely to relapse after weight gain. Furthermore, most previous studies of postcessation weight gain interventions failed to even report the race/ethnic composition of their sample (17), let alone focus on recruiting a diverse sample, as we plan to do. For these reasons, we expect our proposed interventions, if as effective as expected, will make a significant public health contribution to curtailing escalating obesity in this vulnerable population.

3. Study/ Project Population

In this study, we will determine whether two very promising methods of reducing postcessation weight gain, namely a weight stability intervention versus a weight loss intervention followed by a smoking cessation intervention, are efficacious for reducing postcessation weight gain. Given the negative health implications of weight gain after smoking cessation and the difficulty in reducing postcessation weight gain in previous interventions, **we propose the following:**

To randomize up to 400 smokers to 1 of 3 arms: a) a weight stability intervention prior to cessation (Group 1); b) a weight loss intervention prior to cessation (Group 2); or c) a self-guided weight management prior to cessation (Group 3) and to determine the efficacy of the interventions on preventing weight gain at 12 month follow-up. All 3 conditions receive a highly efficacious behavioral smoking cessation program and 6 months of varenicline pharmacotherapy (ChantixTM), the most efficacious medication for smoking cessation (21, 22). Since smoking cessation and body weight are confounded, smoking cessation status and duration of cessation will be examined as covariates.

Inclusion Criteria:

- Participants must be 18 years or older
- Participants must wish to quit smoking in the next 30 days
- Participants must have smoked 5 or more cigarettes a day for at least 1 year

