- Participants must have a self-reported BMI of 22 kg/m² or greater, as it would not be recommended to have those who are underweight or the lower end of the normal BMI range attempt a 5% weight loss (if assigned to Group 2)
- Participants must have access to a telephone and daily access to email. If using a cell phone, participants must be willing to use their cell phone minutes for weekly phone interventions as well as for some or all of the remote data collection visits
- All women of childbearing age must have a negative pregnancy test and must agree to use contraception during participation in the study
- Participants must also be willing to be randomized to the study conditions and wait eight weeks prior to beginning smoking cessation (during which they will participate in the weight management intervention to which they are assigned)
- Participants must have blood pressure that is < 150/95 mmHg and heart rates of >40 beats per minute and <120 beats per minute (according to their health care provider)
- Participants must be able to exercise for at least 10 minutes
- Participants must also have the ability to understand the consent process in English

Exclusion Criteria:

[figure not shown]
- Have a known contraindication, allergy or hypersensitivity to Varenicline

- Are currently (in the previous 30 days) participating in other behavioral or pharmacologic weight or smoking cessation interventions
- Have used an investigational drug within the last 30 days
- Have current suicidal thoughts or have a lifetime history of a suicide attempt as defined by the Columbia-Suicide Severity Rating Scale (C-SSRS) (76)
- Have a self-reported history of psychosis, bipolar disorder or anorexia nervosa
- Self-report current alcohol abuse or illicit substance use
- Have kidney disease or liver disease; HIV; have unstable cardiovascular conditions, or have history of cancer in the last 5 years
- Taking medications that impact weight (see list)
- History of gastric bypass, stomach stapling, banding or other weight loss surgery
- Lost \geq 10 pounds in the last 6 months
- Have another member of their household already participating in this study
- Pregnancy within the last 6 months, breastfeeding or planning to become pregnant during the study follow-up time (12 months)
- Weight limit of 385 pounds

4. Research Design

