Behavioral Smoking Cessation Intervention. Participants in all conditions will get our evidence-based in-person 6 session group-based smoking cessation intervention (44, 45, 89). Participants will transition to the smoking cessation intervention at week 9; they will receive the smoking cessation intervention with the same group with whom they received the weight management intervention, in order to preserve group social support as well as reduce contamination concerns. First, we will prepare participants for the quitting process, including providing varenicline at the first session. We will guide them through setting a quit date, implementing smoking cessation "rituals" (e.g., getting rid of ashtrays), reducing the number of cigarettes per day, and what to expect when they quit (e.g., withdrawal symptoms). By anticipating these issues, participants are able to better cope with them when they do arise. The second phase is the actual quitting process and getting through the first several days of being a nonsmoker. Given that this is the most difficult phase for participants (and is when the most relapse occurs), we will schedule an

individual telephone call during this week for problem solving with the participant. Finally, we will discuss both short-term and long-term relapse prevention strategies in the third phase.

Pharmacologic Intervention. All participants will receive varenicline (i.e., Chantix™) in conjunction with the behavioral smoking cessation intervention. All participants will receive varenicline 0.5 mg once daily for 3 days, increasing to 0.5 mg twice daily for days 4 to 7, and then to the maintenance dose of 1 mg twice daily for a total of 6 months of treatment.

Booster Weight Management Sessions: Participants randomized to Group 1 and 2 will receive monthly booster weight management sessions, after completing the 6-week behavioral smoking cessation intervention. There will be 5 booster sessions (week 16, 20, 24, 28, and 32) that will focus on problem solving related to weight management. Participants will receive the booster sessions with the same group with whom they received the weight management and smoking cessation interventions, in order to preserve group social support as well as reduce contamination concerns. We decided to focus these booster sessions on problem solving for both Group 1 and 2.

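### The SAP has no term for delivery group or wave: the abstinence tests assume independent participants, and for weight the word *mixed* is left undefined.

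*SAP*

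**What the plan says.** Protocol section 5 (Behavioral Smoking Cessation Intervention) states: "Participants in all conditions will get our evidence-based in-person 6 session group-based smoking cessation intervention". Membership is carried over from the first phase: "they will receive the smoking cessation intervention with the same group with whom they received the weight management intervention", and the reason given is "in order to preserve group social support as well as reduce contamination concerns". Groups 1 and 2 then keep it for five boosters ending at week 32: "Participants will receive the booster sessions with the same group with whom they received the weight management and smoking cessation interventions".

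The SAP's single section, Statistical Analysis, never mentions delivery group, wave, clustering or a random effect.

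- **Weight:** "Two separate general linear and mixed ANCOVA-like regression models for continuous measures will be utilized". Only the final weight is modelled, with an adjustment for the fitted difference between arms at baseline. Three contrasts are each tested at .017.
- **Abstinence:** a chi-square test, then a logistic regression with BIBLIO as reference, at .05.
- **Missing outcomes:** imputed by arm.

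Two other statements bear on the size of any correlation. The inclusion criteria in Protocol section 3 say "participants must be willing to use their cell phone minutes for weekly phone interventions", which does not match in-person groups. The same section says "Since smoking cessation and body weight are confounded, smoking cessation status and duration of cessation will be examined as covariates".

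**The concern.** Keeping people together for social support implies that group members influence one another, which is how within-group correlation arises. Groups sit inside arms (clear for Groups 1 and 2, inferred for Group 3), so any effect specific to a group adds to the variance of the arm contrasts. A test that ignores it uses standard errors that are too small.

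The two outcomes differ. Following the abstinence plan as written means assuming independence. For weight, one analyst could fit a plain ANCOVA, another a participant effect over baseline and 12 months, and a third a delivery-group effect. All three would comply, and their standard errors could differ. What is at stake is mainly the two efficacy contrasts. For SMALL against LOSS and for abstinence the plan predicts no difference, so extra rejections there would be false differences.

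**Working it through.** **The plan's own figures.** The allocation reproduces: 400 × 2/5 = 160, 400 × 2/5 = 160, 400 × 1/5 = 80. The level .017 is .05/3 = .0167 rounded. No power calculation is given, so there is none to reproduce.

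**Assumptions, because the documents do not give these inputs.**

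- One group per arm per wave, complete data, no covariates, two-sided tests.
- Layout A: 10 waves of 16/16/8, that is 40 per wave at 2:2:1 (160/160/80).
- Layout B: 20 smaller, more evenly split waves of 7/7/6 (140/140/120).
- ICC of .01, .03 or .05.
- 25% abstinent.

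**Weight, group ignored.** Let ρ be the total within-group correlation and ρg the part specific to arm within wave. The rest is shared by all arms of a wave and cancels from the contrast when the allocation ratio is constant. The true variance of a contrast relative to the variance used is

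R = {[1 − ρ + m1·ρg]/n1 + [1 − ρ + m2·ρg]/n2} / (1/n1 + 1/n2),

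and the true level is 2[1 − Φ(2.387/√R)], where 2.387 is the normal quantile for .017.

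Active arm against BIBLIO, layout A, ρ = ρg = .05: the brackets are .95 + 16 × .05 = 1.75 and .95 + 8 × .05 = 1.35. So R = (1.75/160 + 1.35/80)/(1/160 + 1/80) = (1.75 + 2 × 1.35)/3 = 1.483, and 2.387/1.218 = 1.960 gives .050.

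| Case | Layout A: R, level | Layout B: R, level |
|---|---|---|
| ICC 0 | 1.000, .017 | 1.000, .017 |
| .01, all at group level | 1.097, .023 | 1.055, .020 |
| .03, all at group level | 1.290, .036 | 1.164, .027 |
| .05, all at group level | 1.483, .050 | 1.273, .034 |
| .05, half common to wave | 1.217, .031 | 1.112, .024 |
| .05, all common to wave | 0.950, .014 | 0.950, .014 |

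Simulated null trials agree: .022/.036/.050 (A) and .020/.027/.035 (B) for the three group-level rows, .032 and .023 for the half-and-half row, and about .015 for the last.

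**Abstinence, group ignored.** From 40,000 beta-binomial null trials per cell, the three-arm chi-square at nominal .05 has a true level of about .070/.112/.153 (A) or .058/.078/.099 (B) at ICC .01/.03/.05, all at group level. A repeat run agreed within .003. At ICC 0 it gave .050 and .048. With an ICC of .05 wholly common to the wave it gave .044 and .045, so no inflation.

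**Does a group term repair the weight test?** A random intercept for group, variance not bounded at zero, Satterthwaite degrees of freedom and no wave term gave .016 to .018 for active against BIBLIO when all correlation is at group level. When waves share correlation, a group-mean test standing in for it without a wave term is too conservative, at about .003 to .012. Adding wave gave .014 to .019 in every cell tried.

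**Does by-arm imputation matter?** With 20–30% missing and imputed by arm, the random-intercept test (no wave term) ran at .012 to .021. Adding group indicators to the imputation gave .004 to .007.

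**The case against.** The strongest reply is that the size is guesswork. The ICC, its split, the group sizes and the number of groups per wave are all assumed. There are reasons for a small ICC: the eligibility criteria mention weekly phone contact, no group weight sessions are described for Group 3, boosters stop at week 32, well before the 12-month outcome, and smoking status and other covariates may absorb part of it. If covariates halve an ICC of .05, the level is about .032 (A) or .025 (B). Correlation shared across a wave does not inflate the contrasts at all. All of this stands, so the group-level rows are the upper case and not an estimate. None of it shows that the group-specific correlation is zero.

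A reader might infer that the weight model itself wrongly assumes independence. The documents do not support that. *Mixed* may refer to delivery group. The adjustment for the baseline difference also fits a participant effect over baseline and 12 months. What can be said is that the term is unspecified.

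A reader might also infer that imputing by arm leaves a group-adjusted test too liberal. The range above does not show that in general: .012 to .021 lies on both sides of .017.

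Finally, a group term costs power even if the ICC is 0. That is true and is counted below.

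**Conclusion.** The omission is certain; its size is not. For abstinence, the named tests assume independence in a trial that deliberately keeps participants in groups. For weight, one word needs a definition. If correlation is specific to arm within wave, with ICC .01 to .05, the true level is about .020 to .050 at nominal .017 for each active arm against BIBLIO, and about .058 to .153 at nominal .05 for the abstinence chi-square. At ICC .05 with half common to the wave, the weight level is about .032 (A) or .023 (B). With all of it common to the wave, or none at all, nothing is inflated. These figures rest on one group per arm per wave, the two assumed layouts and complete data; the wave cancellation also needs a constant allocation ratio. The claim that the primary error rate is tripled would need the top of the range and is not supported as a finding. This is a cheap improvement, held with moderate confidence.

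**What to change.** **Weight.** State that the model for 12-month weight (or change) includes wave, fixed or random, and a random intercept for delivery group (arm within wave), with the group variance not bounded at zero and Satterthwaite or Kenward-Roger degrees of freedom. Wave is also needed because Protocol section 5 lets the allocation ratio change in waves under 40. If baseline and 12-month weights are modelled jointly, use a group-by-time random effect: a group intercept common to both times cancels from the change contrast and corrects nothing.

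**Abstinence.** Replace the plain chi-square with one scaled by between-group dispersion and referred to an F distribution. It ran at .048 to .051 when all correlation was at group level. Remove wave-level variation first, or it becomes conservative. Fit the logistic model with wave included and a Mancl-DeRouen small-sample variance clustered on delivery group (.042 to .045 when checked without wave or covariates). The Kauermann-Carroll correction ran at .057 to .059 in layout A. A random-intercept logistic model was not simulated.

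**Imputation.** By-arm imputation can stay; do not add group indicators to it.

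**Delivery mode.** Protocol section 3 (phone) and section 5 (in-person groups) must be reconciled, since the answer decides what the cluster is.

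**Cost.** SAP wording and a few lines of code, provided group membership was recorded, plus somewhat wider intervals. For an effect with 80% power under independence, the noncentrality is 2.387 + 0.842 = 3.228. In layout A, 30 groups less 3 arms leave 27 df, a critical value of 2.544 and power of about .75 at ICC 0, rising to about .78 with Satterthwaite df. With 18 df (critical value 2.630) it is about .72. That can arise from a separate BIBLIO variance, or from a fixed wave effect in a group-mean analysis, where 9 further df go. So the loss at ICC 0 is from .80 to about .72–.78, with nothing gained in that case.

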Efficacy of Two Novel Behavioral Post-cessation Weight Gain Interventions

NCT03156660

Document Uploaded 21APR2022

Document Created 10NOV2020

1. Purpose

Although smoking cessation accrues significant health benefits, regardless of the duration of smoking (4, 25, 26), it is typically accompanied by weight gain. A recent meta-analysis quantified this weight gain as, on average, 1.1 kg, 2.3 kg, 2.9 kg, 4.2 kg, and 4.7 kg at 1, 2, 3, 6, and 12 months after quitting, respectively (9). Concerns about postcessation weight gain are common and are often cited as a reason to delay cessation attempts (10, 11); furthermore, postcessation weight gain is associated with smoking relapse (10-12).

While there is some ongoing debate (13-15) about the effectiveness of behavioral weight management programs in conjunction with smoking cessation programs, it appears that behavioral weight management programs have not been able to successfully reduce postcessation weight gain (16). In addition, contrary to popular belief, there was no indication that involvement in weight management programs impacted abstinence (16, 17). Moreover, while some short-term weight gain attenuation has been observed with some pharmacotherapies (e.g., nicotine replacement therapy, varenicline), there is no long-term weight gain prevention benefit for any of the pharmacotherapies (27-30).

Much like weight maintenance after weight loss has proven to be challenging (18), weight maintenance after smoking cessation has been difficult to achieve. In a trial unrelated to postcessation weight gain, Wing and colleagues (19) hypothesized that making small, consistent changes may be beneficial for weight gain prevention. Wing *et al.* (19) tested this hypothesis in a recent study and found that participants who received their 'Small Changes' intervention gained significantly less weight as compared to the control group. Given these positive results, this approach may be translated to interventions focusing on other individuals at high risk for weight gain (i.e., those who are about to undertake smoking cessation).

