Why Do You Smoke: We will utilize the “Why Do You Smoke?” questionnaires that was adapted for assessing smoking specific weight concern. The scale shows evidence of predictive validity. A score of 7 or below indicates a low level of weight concern, whereas a score of 22 or greater indicates a high level of smoking specific weight concern. Participants will complete this 18-item measure by indicating their degree of agreement on a 6-point scale.

Self-Efficacy: We are assessing general self-efficacy with the Self-Performance Survey short form. These 4 items are rated on a 5-point scale.

Treatment Preference: We are assessing participants' preference for each of the treatment conditions at baseline to explore whether match or mismatch to treatment preference influenced outcome.

Weight Concern: We will measure participants weight concerns related to smoking. The 6 items on this scale are scored on a 10-point scale.

Return to Smoking: The 11 item scale (63) will be used to assess the degree of weight loss that may precipitate a return to smoking. Participants are asked if they would return to smoking after a gain of less than 2 pounds, and each subsequent question adds 2 pounds until the participant is asked, "If after quitting smoking you gained 20 pounds or more, would you start smoking?" Those that indicate that they would return to smoking after any weight gain will be classified as "weight concerned."

Importance of Weight and Smoking Cessation: The extent to which participants prioritized weight control and smoking cessation will be measured using 2 items rated on 10-point scales.

Smoking Behaviors: We will assess nicotine dependence with the Fagerström Test for Nicotine Dependence (100) and smoking status (both point prevalence and prolonged abstinence). For those participants who report point prevalence abstinence, we will test cotinine levels. Cotinine, a direct metabolite of nicotine, will be measured using the iScreen® OFD Cotinine test. iScreen is a valid and reliable method for verifying smoking status, with a specificity of >99%, a sensitivity of 97.6%. We will consider participants with at least 30 ng/mL cotinine in their saliva to be smokers; this liberal definition will avoid false positives due to secondhand smoke.

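### Smoking status, which arises after randomisation, is put into the modelling of the main 12-month weight comparison as moderator or confounder, and no main model without it is named

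*SAP*

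**What the plan says.** The SAP's weight paragraph takes change in weight from baseline to 12 months as the outcome and assigned arm as the exposure. It describes ANCOVA-like models with the "treatment effect estimated as the distance between the fitted group-specific means at the 12-month data collection visit", adjusted for the baseline difference, demographic factors, baseline weight and further covariates if needed. It then plans interaction tests between arm and demographics, and continues: "We will include smoking status within our modeling strategy either as moderator or a confounder". The third contrast, SMALL against LOSS, is to be made within the same models. The paragraph closes with the .017 level for the three planned contrasts and .05 for everything else.

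Protocol section 3 points the same way. It calls cessation and body weight confounded and says that "smoking cessation status and duration of cessation will be examined as covariates". The SAP does not mention duration of cessation.

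The Protocol's Smoking Behaviors measure records both point-prevalence and prolonged abstinence. The SAP specifies prolonged abstinence for the cessation outcome, but does not say which status, or which time point, is meant in the weight model.

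**The concern.** A confounder of a randomised comparison would have to precede assignment. Cessation status does not. It lies downstream of the arm and could be part of how the arm affects weight. Conditioning on it can remove part of the arm's effect. If something unmeasured drives both quitting and weight, conditioning can also introduce bias that randomisation had excluded.

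As a moderator, it leaves the difference between fitted group means undefined until someone decides how abstainers and smokers are weighted. With the role, the definition and the weights all unstated, several different results could be put forward as the main one, and the choice would be made after the data are seen.

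**Working it through.** **Timing.** Entry requires current, established smoking: "Participants must have smoked 5 or more cigarettes a day for at least 1 year". Treatment to quit comes after the randomised 8-week weight phase: "Participants will transition to the smoking cessation intervention at week 9". Variation in cessation status therefore arises after randomisation. An effect of arm on it is plausible on the Protocol's own account, because "postcessation weight gain is associated with smoking relapse" and the arms are designed to change weight.

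**Use as a covariate.** With additive effects, randomised effect − adjusted effect = (difference in abstinence) × (weight gap, quitters minus continuing smokers).

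- Gap: Protocol section 1 cites gains of 4.2 kg at 6 months and 4.7 kg at 12 months after quitting. Someone who quits soon after week 9 has been abstinent for about 10 months at the 12-month visit: 4.2 + 0.5 × (10 − 6)/(12 − 6) = 4.53 kg. Using this as the gap assumes no gain in continuing smokers, so it is an upper-end figure; 3.0 kg is an assumed lower value.
- Abstinence differences: 5 and 10 points, assumed.

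| Abstinence difference | Gap 3.0 kg | Gap 4.53 kg | Gap 4.7 kg |
|---|---|---|---|
| 5 points | 0.15 kg | 0.23 kg | 0.24 kg |
| 10 points | 0.30 kg | 0.45 kg | 0.47 kg |

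A large-sample simulation (2,000,000 subjects, direct effect −2.0 kg, gap 4.53 kg, 25% abstinent in the control arm) agrees:

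| Active arm's abstinence | Randomised effect | Adjusted estimate |
|---|---|---|
| +5 points | −1.77 kg | −1.99 kg |
| −5 points | −2.23 kg | −2.00 kg |
| Equal | −2.01 kg | −2.01 kg |

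**Shared cause.** Assume instead no direct arm effect, a 4.7 kg gap, control abstinence of 20–30%, and an unmeasured factor worth 1–2 kg per SD that also drives quitting. For abstinence differences of 5, 10 and 15 points, the randomised effect is about +0.23, +0.47 and +0.71 kg. The adjusted estimates are about −0.05 to −0.09, −0.08 to −0.17 and −0.12 to −0.25 kg, which is the opposite sign.

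**Scale.** Protocol section 5 plans 160 participants in each active arm and 80 in the control arm. With an assumed SD of 5.5 kg, SE = 5.5 × √(1/160 + 1/80) = 0.75 kg. A 0.23 kg shift is 0.23/0.75 ≈ 0.3 SE.

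**Use as a moderator.** Assume effects of −1.5 kg in smokers and −3.0 kg in abstainers, with 25% abstinent in both arms.

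- Observed-margin weights: 0.75 × (−1.5) + 0.25 × (−3.0) = −1.88 kg, which equals the randomised effect.
- Equal weights: 0.5 × (−1.5) + 0.5 × (−3.0) = −2.25 kg.
- With −1 and −4 kg, the two results are −1.75 and −2.5 kg.

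**Open choice.** This simulation used 6,000 null trials of 160 against 80, residual SD 5.5 kg, with point prevalence of 30% and prolonged abstinence of 20% (nested), equal in both arms; these rates are assumed. Each definition entered as a covariate, as a moderator with observed weights, and as a moderator with equal weights, giving six analyses.

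- Each analysis alone rejected at .017 in 1.4–1.9% of trials.
- At least one of the six rejected in 3.4% (Monte Carlo SE about 0.2 points).
- The six estimates spread by a median of 0.55 kg (90th percentile 1.08 kg).

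A repeat with the 4.53 kg gap tied to prolonged abstinence gave:

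| Analyses allowed | At least one p < .017 | Median spread |
|---|---|---|
| All six | 3.5% | 0.57 kg |
| Both definitions, no equal weights | 1.9% | 0.13 kg |
| Prolonged abstinence only, all three uses | 2.6% | 0.39 kg |
| Prolonged abstinence only, no equal weights | 1.6% | 0.01 kg |

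**The case against.** The best defence is that the SAP describes a baseline-adjusted model first and attaches the treatment effect to it. The smoking sentence follows the interaction tests, so the moderator role could be read as more heterogeneity testing. The SAP also separates the main comparisons at .017 from other associations at .05, and commits to intention to treat regardless of smoking status. This reading is possible, but the text does not secure it. The sentence is a commitment, it sits before the .017 rule, no model is labelled as main, and calling status a confounder implies adjustment. The intention-to-treat sentence settles who is analysed, not which terms enter the model.

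A second objection is that every arm receives the same cessation programme and varenicline, and the SAP expects that the arms "will have similar rates of smoking cessation at 12-month assessment". Under equal rates and additive effects the covariate shift is near zero, and that stands. But similar rates are a hypothesis under test, so the main model cannot depend on them.

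Third, the 3.4% depends on options that the documents do not list. Equal stratum weights appear in neither, and the figure assumes that the most favourable result is picked. This stands as a limit: without equal weights the excess nearly disappears. The figure shows what the silence permits and does not predict what would be done.

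**Conclusion.** The concern holds. As written, the plan allows the main weight result to be one adjusted for a post-randomisation variable, and such a result need not equal the randomised effect.

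The likely size is modest: about 0.15–0.24 kg per 5 points of difference in abstinence, against an assumed SE of 0.75 kg. It is larger, with a possible change of sign, if abstinence differs more and quitting and weight share a cause. The SD, abstinence rates, stratum effects and quitter–smoker gap are assumptions; only the 4.2 and 4.7 kg gains and the planned allocation come from the documents.

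The case rests at least as much on the undefined main estimate as on the size of the shift.

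**What to change.** In the SAP, name one main model for all three .017-level contrasts, containing arm and pre-randomisation covariates only: baseline weight, listed demographics and, if wanted, baseline smoking history. State that no variable arising after randomisation enters it.

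Keep the analyses by 12-month smoking status, and by duration of cessation if still wanted, as labelled supplementary, non-randomised analyses. For each, fix the abstinence definition, the time point, the role of the variable and the stratum weights in advance. Amend the matching sentence in Protocol section 3. Place the abstinence-by-arm results that the SAP already plans beside the weight result.

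The cost is wording, with two downsides. An arm with fewer quitters can look better on weight, which is why abstinence must be shown alongside. Some precision is also given up: in the simulation the SE was about 0.79 kg without smoking status and 0.76 kg with it.
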